## What is already known on this subject? AND

## What does this study add?

Near normalization of blood glucose levels has been known to reduce the long-term risk of diabetic retinopathy. However, transient worsening of preexisting retinopathy has also been demonstrated when glucose control is intensified (**Bethel A. et al., 2021**).

The pathophysiology of this phenomenon is not well understood. Furthermore, the circumstances under which it appears remain to be not fully elucidated. Since its discovery, early worsening has been described in patients with type 1 and type 2 diabetes, including those undergoing various diabetic therapies, those who have undergone bariatric surgery, and pregnant women (**Feldman-Billard et al., 2018**).

Hence, this study will assess the relationship between the glycemic control in patients with diabetes mellitus and the contemporary statements on the value of tight glycemic control, when compared with less tight control with regard to microvascular outcomes including diabetic retinopathy, nephropathy and neuropathy.

## 1. INTRODUCTION/ REVIEW

Diabetes mellitus (DM) is a metabolic disorder characterized by chronic hyperglycemia due to either insulin deficiency or resistance or both (**Goyal & Jialal 2021**). Hyperglycemia induces tissue damage through mitochondrial superoxide production, affecting retina, glomerulus, and neurons. It requires continuing medical care and ongoing self-care management to prevent and delay acute and long-term micro and macrovascular complications (**Fasil A et al., 2019**).

Chronic diabetes complications like retinopathy, nephropathy, neuropathy, self-reported chest pain, vision decrement, painful paresthesia, and psychiatric

events result in decrement of health-related quality of life (**Jacobson *et al.*, 2013**).

Diabetic retinopathy (DR) is the most common microvascular complication of DM and is a leading cause of blindness in the working age population worldwide (**Leasher *et al.*, 2016**). It is a progressive sight-threatening eye disease caused by hyperglycemia, which damages the retinal microvasculature leading to vascular permeability, retinal ischemia, neovascularization, retinal detachment, and blindness (**Augustine *et al.*, 2020**).

After the DCCT (Diabetes Control and Complications Trial) found that tight glycemic control (a glycohemoglobin A1c (HbA1c) <7% ) could prevent or slow the progression of nephropathy, retinopathy, and neuropathy in patients with diabetes mellitus, a consensus, extended to patients with type 1 and type 2 diabetes mellitus, emerged: normalizing glycemia prevents diabetes mellitus complications (**Garber *et al.*, 2013**). Guidelines, quality improvement interventions, quality-of-care measures and patient-directed marketing have since focused on achieving tight glycemic control. (**Rodriguez & Montori 2016**).

Appropriate glycemic control and management is fundamental to prevent and delay DM complications. Poor glycemic control is highly correlated with high burden of diabetes complications. However, data are scanty regarding factors for poor glycemic control and the relationship between glycemic control and DM complications (**Fasil A *et al.*, 2019**).

## 2.AIM / OBJECTIVES

This randomized controlled study will examine the relation between tight glycemic control and microvascular complications of Diabetes in comparison with patients with good (less tight) glycemic control.

**Research question:** Does tight glycemic control worsens microvascular complications of Diabetes?

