### 3.METHODOLOGY:

#### **Patients and Methods/ Subjects and Methods/ Material and Methods**

- **Type of Study:**

Randomized controlled trial.

- **Study Setting:**

The study will be conducted at Ain Shams University Hospitals “outpatient diabetes clinic and inpatient department.”

- **Study duration:**

This study will be conducted during the period from May 2022 to October 2023

- **Labs (see later), thorough clinical examination with special emphasis on microvascular complications (neurological and Fundus examination) will be done for every patient at time of recruitment and 6 months following glycemic control.**

- **Study Population:**

- 80 subjects with uncontrolled Diabetes Mellitus with HbA1c 8% or above all will receive standard medical care (nutritional therapy and pharmacological therapy) and will be divided into two groups:
  - (a) Group (A) will undergo tight glycemic control (HbA1c <7%) done by nutritional education and medication adjustment.
  - (b) Group (B) will undergo conventional glycemic control (HbA1c <7.5 %).

Subjects will be collected from patients with Diabetes Mellitus referred to Ain Shams University Hospitals for evaluation with the following criteria:

- **Inclusion criteria:**

1. Both sexes.
2. Age 18-60years old.
3. Patients diagnosed with Diabetes Mellitus (Type 2) according to ADA guidelines.
4. Patients willing to participate after signing a written consent to be enrolled in the study after being explained to them in an interview.
5. Diabetic patients with mild and moderate non proliferative diabetic retinopathy

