## **Sample Size:**

The study will be conducted on 80 subjects.

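### Does a contrast of HbA1c <7% against <7.5% in 80 subjects fail to answer whether tight control worsens complications?

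*Protocol*

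**What the plan says.** The introductory section (What does this study add?) notes that "transient worsening of preexisting retinopathy has also been demonstrated when glucose control is intensified". It then describes tight control "when compared with less tight control with regard to microvascular outcomes". Section 2 (Aim / Objectives) sets patients under tight control "in comparison with patients with good (less tight) glycemic control", and the line beneath gives the research question, "Does tight glycemic control worsens microvascular complications of Diabetes", without a comparator. The Outcomes line under Study procedures and interventions also names tight control alone.

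Study Population, in section 3, enrols "80 subjects with uncontrolled Diabetes Mellitus with HbA1c 8% or above", all of whom receive standard care. It defines the arms: "Group (A) will undergo tight glycemic control (HbA1c <7%) done by nutritional education and medication adjustment"; "Group (B) will undergo conventional glycemic control (HbA1c <7.5" %). Under Sample Size the whole statement is "The study will be conducted on 80 subjects". No power, effect size, worsening rate, margin or allocation ratio is stated.

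**The concern.** The trial is motivated by retinopathy getting worse when control is tightened, yet control is tightened in both arms. Whatever harm the shared lowering causes appears in both groups and drops out of the difference A minus B. What is left is the extra effect of a ceiling 0.5 points lower.

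Taken alone, the research question reads as a test of tight control itself. With 80 subjects and a narrow contrast, a non-significant difference is quite possible even if lowering does worsen retinopathy. A reader could then answer the question with a plain no. Every participant already has mild or moderate retinopathy, so that would be false reassurance on the safety issue behind the trial. The sample size is given without any account of what it can show or exclude.

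**Working it through.** **Inputs from the protocol.** Entry HbA1c 8% or above; ceilings 7% and 7.5%; 80 subjects; two-sided significance at 0.05. The figure of 80 cannot be reproduced, because no inputs to it are stated.

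**Assumptions, not in the protocol.** 40 per arm, no losses, worsening counted as yes or no, and a range of worsening rates.

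**1. Size of the contrast.** The ceilings differ by 7.5 − 7.0 = 0.5 points. If each arm just reached its ceiling:

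| Entry HbA1c | Fall in A | Fall in B | B as share of A |
|---|---|---|---|
| 8% | 1.0 | 0.5 | 50% |
| 9% | 2.0 | 1.5 | 75% |
| 10% | 3.0 | 2.5 | 83% |

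Half or more of the fall is shared. Neither target has a floor, so actual separation could differ from this.

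**2. What an exact null leaves open.** With the same observed rate p in both arms and n = 40, the 95% limits for the risk ratio are exp(±1.96 × √(2(1 − p)/(np))). At p = 0.10 this is exp(±1.96 × √(1.8/4)) = exp(±1.315), or 0.27 to 3.72.

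| Rate in each arm | Risk ratio, 95% limits |
|---|---|
| 5% | 0.15 to 6.76 |
| 10% | 0.27 to 3.72 |
| 20% | 0.42 to 2.40 |
| 30% | 0.51 to 1.95 |
| 40% | 0.58 to 1.71 |

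The upper limit equals 2.0 at a rate of about 29%. The Newcombe interval for the risk difference is ±12 points at 5%, ±14 at 10% and ±18 at 20%. Adding the upper limit to Group B's observed rate and dividing by that rate gives smaller multiples, for example (0.10 + 0.144)/0.10 = 2.4 at 10%. That treats Group B's rate as known, so the risk-ratio limits are the ones to use.

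**3. Power for a true doubling, 40 per arm.** About 13% at a control rate of 5%, 24% at 10%, 50% at 20% and 78% at 30%. For 80% power the pooled-variance formula needs 199, 82 and 42 per arm at 10%, 20% and 30%.

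**4. An unfavourable illustration.** Suppose worsening is proportional to the fall, so that risk in A = risk in B × (b − 7)/(b − 7.5) for entry value b. From b = 9 the ratio is 2.0/1.5 = 1.33, and 10% in B becomes 13.3% in A. Exact power is about 7%, and 80% power needs 1,455 per arm. From b = 8 the ratio is 2.0, and with 20% in B exact power is about 50%. The answer depends heavily on assumptions that the protocol neither makes nor contradicts.

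**5. Continuous measure.** The 95% half-width is t(78, 0.975) × √(2/40) = 0.445 SD. Power is about 80% at a true difference of 0.63 SD.

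**6. The wording side by side.** The aim states tight against less tight. The introductory section states the same comparison. Study Population gives both figures. The question and the Outcomes line omit the comparator, but neither names a different one.

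**The case for a change.** The strongest case for change is that the research question and the sample size are protocol content, so an unseen analysis plan does not excuse them. Rewording costs almost nothing. A protocol that fixes 80 subjects should say what that number can exclude, or call the trial exploratory. At worsening rates of 20% or less, the interval after a null result would be too wide to support a plain no.

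Part of this stands. The randomised contrast is only the lower target against the higher one. The number 80 has no derivation. At low rates the trial is imprecise, and a non-significant result would not show absence of harm.

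It does not amount to a needed change. The missing comparator is in the sentence immediately above the question, and a one-line question beneath a full aim is shorthand. Shared lowering cancels in any comparison of two targets and is not a fault of this one. No power or margin is claimed, so the sample size contradicts nothing. A derivation would need a worsening rate that the protocol does not give, and it would either describe the same 80 subjects or call for more. At 10% against 20% that means 199 per arm, or 398 in all, nearly five times the planned size, in a study the investigator pays for. How a non-significant result is read, and with what interval, is commonly settled in the statistical analysis plan.

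**Conclusion.** The concern describes the trial correctly but does not call for a change. The comparison of <7% with <7.5% is valid, is stated as tight against less tight in the aim and the introductory section, and is defined in Study Population. The comparator's absence from the question and the Outcomes line is a gap in wording that any analyst fills from the sentence above; filling it alters no estimate, interval or test.

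The imprecision is real, but its size rests on assumptions: with 40 per arm, no losses and a yes/no outcome, an exact null leaves an upper risk-ratio limit from 6.8 at 5% worsening down to 1.7 at 40%, with a doubling excluded only above about 29%. With 20% losses (32 per arm) the upper limits at 10%, 20% and 30% rise to 4.35, 2.66 and 2.11. A small trial of this kind is a fair trade-off for a self-funded study, provided the report gives the between-arm difference in complications with its 95% interval alongside the achieved HbA1c separation. Both follow from data already collected. This conclusion takes no view on either HbA1c target.

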### 3.METHODOLOGY:

#### **Patients and Methods/ Subjects and Methods/ Material and Methods**

- **Type of Study:**

Randomized controlled trial.

- **Study Setting:**

The study will be conducted at Ain Shams University Hospitals “outpatient diabetes clinic and inpatient department.”

- **Study duration:**

This study will be conducted during the period from May 2022 to October 2023

- **Labs (see later), thorough clinical examination with special emphasis on microvascular complications (neurological and Fundus examination) will be done for every patient at time of recruitment and 6 months following glycemic control.**

- **Study Population:**

- 80 subjects with uncontrolled Diabetes Mellitus with HbA1c 8% or above all will receive standard medical care (nutritional therapy and pharmacological therapy) and will be divided into two groups:
  - (a) Group (A) will undergo tight glycemic control (HbA1c <7%) done by nutritional education and medication adjustment.
  - (b) Group (B) will undergo conventional glycemic control (HbA1c <7.5 %).

Subjects will be collected from patients with Diabetes Mellitus referred to Ain Shams University Hospitals for evaluation with the following criteria:

- **Inclusion criteria:**

1. Both sexes.
2. Age 18-60years old.
3. Patients diagnosed with Diabetes Mellitus (Type 2) according to ADA guidelines.
4. Patients willing to participate after signing a written consent to be enrolled in the study after being explained to them in an interview.
5. Diabetic patients with mild and moderate non proliferative diabetic retinopathy

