**Exclusion criteria:**

1. Patients with age above 60 or below 18 years old.
2. Patients with severe non proliferative diabetic retinopathy up to advanced proliferative diabetic retinopathy.
3. Patients diagnosed with type 1 DM.
4. Patients with malignant tumors.
5. Patients with end stage renal disease and end stage liver disease.
6. Patients with history of myocardial infarction.
7. Patients with recurrent attacks of hypoglycemia and hypoglycemia unawareness.

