## **Study procedures and interventions:**

1. After approval of study protocol, patients will be enrolled into the study according to inclusion and exclusion criteria.
2. All participants will sign written informed consent that is approved by the local ethics committee.
3. All patients will be subjected to:
  - **Detailed history taking of the patient medical condition.**
  - **Anthropometric and blood pressure measurements:**
    - ✓ Weight and height of all patients will be measured using a calibrated scale. Body mass index (BMI) will be calculated by dividing weight in kilograms by height in meters squared.

- ✓ Blood pressure will be measured in both standing and seated position after a 5-min rest using an aneroid sphygmomanometer and stethoscope.

- ✓ Basal heart rate measurement

➤ **Biochemical assays:**

- ✓ Laboratory measurements will include:
  - ❖ Fasting, 2 hour post prandial glucose levels and HbA1C.
  - ❖ Kidney function tests including serum urea and creatinine.
  - ❖ Albumin/creatinine ratio.
  - ❖ Estimated GFR calculation using MDRD 4 variable equation.
  - ❖ Complete blood count.

➤ **Fundus examination using Optomed aurora portable fundoscopy.**

➤ **Neurological assessment usingDN4 (Douleur Neuropathique 4 questions).**

- **Labs, neurological and Fundus examination will be done at time of recruitment and 6 months following glycemic control.**

▪ **Outcomes:**

Effect of tight glycemic control on microvascular complications of Diabetes.

▪ **Statistical analysis:**

To summarize characteristics of study patients based on TyG quartiles, one-way analysis of variance (ANOVA) and chi-square ( $\chi^2$ ) tests will be used, where appropriate. To determine the association of liver fibrosis with TyG, multivariable-adjusted odds ratios (ORs) will be applied. Two-sided significance at  $P < 0.05$  will be significant.

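### Does the missing description of how patients are allocated leave the comparison open to selection by retinopathy grade?

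*Protocol*

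**What the plan says.** Two places name the design. Section 2 (Aim / Objectives) says "This randomized controlled study will examine the relation between tight glycemic control and microvascular complications", and Section 3 (Methodology, Type of Study) says "Randomized controlled trial".

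The arms are introduced under Study Population: the 80 subjects receive standard medical care "and will be divided into two groups", one with an HbA1c target below 7% and the other below 7.5%.

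Study procedures and interventions lists three numbered steps:

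1. Enrolment: "patients will be enrolled into the study according to inclusion and exclusion criteria".
2. Consent, given in writing on an ethics-approved form.
3. Assessments for every patient, with laboratory, neurological and fundus examinations at recruitment and again at 6 months.

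None of the three assigns an arm, and no ratio, sequence, concealment or assignment time appears elsewhere in the protocol.

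On retinopathy, the inclusion criteria admit "Diabetic patients with mild and moderate non proliferative diabetic retinopathy" and the exclusion criteria remove "Patients with severe non proliferative diabetic retinopathy up to advanced proliferative diabetic retinopathy". The opening section lists "microvascular outcomes including diabetic retinopathy, nephropathy and neuropathy" as the outcomes of interest.

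**The concern.** A randomised trial draws its validity from the way patients reach their arms, and here that step is described only by its result. Who assigns, when, and whether the next assignment is hidden from recruiters are matters of conduct. They belong in a protocol, and a SAP written later would not normally supply them.

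The setting makes the worry concrete. Retinopathy is both an entry criterion and an outcome, and the fundus is examined at recruitment. The protocol's own rationale is that intensified control may transiently worsen existing retinopathy. A recruiter who believes this, and who can foresee or choose the arm, has a motive to keep more advanced eyes out of the tight-control group. The arms would then differ before treatment, the difference would be read as an effect of treatment, and enlarging the sample would not remove it.

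**Working it through.** **What the text supports**

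| Question | What the protocol gives |
|---|---|
| Is the design randomised? | Yes, stated in Section 2 and in Section 3 |
| How are arms formed? | "and will be divided into two groups", under Study Population; no method |
| Does anything contradict randomisation? | No. Purposive sampling, under Sampling Method, concerns who is recruited, not which arm they enter |
| Is mild versus moderate recorded per patient? | Not stated. Eligibility only separates mild or moderate from severe or worse |
| Who examines or reads the fundus? | Not stated |

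The wording on two groups is compatible with randomisation. That recruiting staff know whether a patient is mild or moderate is plausible, but it is an inference. That they choose the arm is not suggested anywhere.

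**How large the bias could be**

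The protocol has no figure to reproduce here. From it come N = 80 and a two-sided 5% level. Everything else is assumed: half the patients moderate, worsening risk 10% in mild and 20%, 30% or 40% in moderate disease, no true treatment effect, and a binary outcome tested without adjustment. In a fraction f of patients the arm follows the grade, always in the same direction; in the rest it is a coin flip.

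The moderate share then differs between arms by f on average, so

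spurious risk difference = f × (risk in moderate − risk in mild).

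At f = 0.10 this is 0.10 × 0.10 = 1 point up to 0.10 × 0.30 = 3 points. Rejection rates come from 100,000 simulated trials per cell with a pooled two-proportion z test.

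| f | Patients steered | Spurious difference | Rejection rate |
|---|---|---|---|
| 0 | 0 of 80 | 0 | 5.1% |
| 0.10 | 8 of 80 | 1–3 points | 5.3–6.2% |
| 0.20 | 16 of 80 | 2–6 points | 5.7–9.6% |
| 0.40 | 32 of 80 | 4–12 points | 7.8–23.6% |

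A normal approximation checks the middle of the table. Take 40 per arm, moderate shares of 40% and 60%, and risks of 30% (moderate) and 10% (mild).

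- Arm risks: 0.4 × 0.30 + 0.6 × 0.10 = 0.18, and 0.6 × 0.30 + 0.4 × 0.10 = 0.22; the difference is 0.04.
- Null standard error: √(0.20 × 0.80 × 2/40) = 0.0894.
- Standard error under these risks: √[(0.18 × 0.82 + 0.22 × 0.78)/40] = 0.0893.
- Rejection rate: Φ[(0.04 − 1.96 × 0.0894)/0.0893] + Φ[(−0.04 − 1.96 × 0.0894)/0.0893] = 0.065 + 0.008 = 7.3%.

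The simulation gives 7.5% for the same case (f = 0.20, risks 10% and 30%).

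**Whether stratifying by grade would be a clear gain**

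With correct unrestricted randomisation, 40 per arm and a moderate share of 30–70%, the exact binomial probability that the arms differ by at least 20 points in that share is 6.7–9.3%. This is chance imbalance, which the 5% error rate already allows for.

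A list stratified by grade but unrestricted within grade leaves the probability at 5.1–7.6% in simulation, so it buys no real balance. Restriction does: with permuted blocks of 4 and 6, or a cap of 3 on the imbalance, the largest gap in 20,000 simulated trials at each grade mix was 7.5 points. The price is predictability. A recruiter who guesses the less-used arm is right 69% of the time with the blocks and 58% with the cap, against 50% with no restriction.

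**The case for a change.** The strongest case for a change is that allocation governs conduct from the first patient, cannot be repaired in analysis, and would take only a sentence and one more procedural step. Neither an unseen SAP nor the removed front pages explain the silence, because the methodology and procedures sections are shown. The protocol's interest in early worsening also supplies a motive for steering, and a label by itself prevents nothing.

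Much of this stands. The protocol is thin on a point it should cover, and a reader of the results will need to know how patients were assigned before accepting the word randomised. What does not stand is the step from silence to a defect in the design. The text neither says nor implies that arms are chosen. Selection could follow any baseline feature, or none, and singling out retinopathy grade relies on a per-patient record that the protocol does not mention. The higher error rates need 32 of 80 patients steered one way and, for the 23.6% figure, a fourfold risk ratio between grades, with no support for either in the document.

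**Conclusion.** The observation is accurate: no allocation step, ratio or concealment is described. It is missing detail, not an error or a contradiction, and it does not show that allocation is non-random or follows retinopathy grade. Investigators who carry out the stated randomised design fill the gap in the ordinary way, and the trial report is where the method used has to be set out.

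The size of the harm is conditional throughout. With no steering the bias is zero and the test is nominal (5.1% simulated). With 8 of 80 patients steered, under the assumed mix and risks, the false-positive rate is 5.3–6.2%; only much heavier steering moves it far. Stratifying by grade is a design preference: it needs a recorded mild or moderate grade for each patient, helps only if the list is restricted within grade, and makes assignments easier to guess. The plan can stand on this point.

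The conclusion rests on taking the randomised label at its word. Evidence that arms were in fact chosen by staff would overturn it, and the protocol contains none.
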